8.2.2.12. Duration of Treatment

The duration of treatment is calculated as follows:

$$\text{Duration of treatment (months)} = (\text{last nonzero dose date} - \text{first dose date} + 1)/30.4375$$

Duration of treatment will be summarized with descriptive statistics (n, mean, median, mode, standard deviation and range), frequency of occurrence <2months, ≥ 2 months and <4months, ≥ 4 months and <6months, ≥ 6 months and <8months, and ≥ 8 months. Duration of treatment may also be presented graphically.

8.2.3. Safety Analyses

Safety data will be summarized using Pfizer standard data summary procedures. Data will be summarized by cohort, defined by the initial dose. When the initial dose is determined to be the MTD, then the tables will also label the dose as the MTD. A breakdown of demographic

data will be provided for age, race, weight, body mass index, and height by cohort defined by initial dose.

On-treatment period is defined as the time from the first dose of study intervention through the minimum of (90 days (28 days for patients who completed the trial prior to approval of PA8 in June 2021) after last dose and start day of new anticancer therapy) – 1 day. Adverse events occurring on the same day as the first dose of study intervention and marked “After” will be considered to have occurred during the on-treatment period. For all AE analysis relative to dosing time or date, AEs occurring on the same day of dosing but marked “Before” will be attributed to previous dose, and those marked as “After” will be attributed to the dose.

The analysis sets to be used are the Safety Analysis set, DLT Evaluable Set will be used as applicable.

For some summary tables, the following clustered terms for cytopenia based on PT may be used:

- Thrombocytopenia (PT=Thrombocytopenia; Platelet count decreased),
- Anaemia (PT=Anaemia; Haemoglobin decreased, Red blood cell count decreased, Haematocrit decreased, Normochromic anaemia, Normocytic anaemia, Normochromic normocytic anaemia),
- Neutropenia (PT=Neutropenia; Neutrophil count decreased, Neutrophil percentage decreased, Cyclic neutropenia, Agranulocytosis, Granulocytopenia, Granulocyte count decreased), Leukopenia (PT=Leukopenia; White blood cell count decreased),
- Lymphopenia (PT=Lymphopenia; Lymphocyte count decreased, Lymphocyte percentage decreased, CD4 lymphocytes decreased, CD4 lymphocyte percentage decreased, CD8 lymphocytes decreased, CD8 lymphocyte percentage decreased),
- Hyperphosphataemia (PT=Blood phosphorus increased),
- Hypertension (PT=Blood pressure increased).

AE summarized as Peripheral Neuropathy includes MedDRA SMQ Peripheral neuropathy narrow and broad and SMQ Guillain-Barre syndrome narrow.

Hypogammaglobulinemia as an adverse even of clinical interest may be presented, using the following definition MedDRA PT terms: 'Blood immunoglobulin G decreased', 'Hypogammaglobulinaemia', 'Hypoglobulinaemia', 'Immunoglobulins decreased', 'Globulins decreased'.

AE summarized as Infection includes any event from SOC Infections and infestations.

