9.6. Safety Analysis

Summaries and analyses of safety parameters will include all patients in the Safety Analysis Set. For patients who undergo intra-patient dose escalation, safety analysis of their initial assigned dose will be censored at time of intra-patient dose escalation (or maintenance dose escalation for Part 1.1). This will allow at least 60 days of safety analysis for all patients at their initial assigned dose levels.

9.6.1. Analysis of the Primary Endpoint for Part 1

DLT is the primary endpoint of the dose escalation component of the study. The occurrence of DLTs observed in the dosing cohorts is used to estimate the MTD/MAD as described in the Study Design [Section 3](#). Adverse Events constituting DLTs will be listed per dose level.

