2. INTRODUCTION

This document describes the planned statistical analyses for Protocol C1071001 latest amendment, dated 06 Jun 2021. This SAP is meant to supplement the study protocol. This SAP supersedes the statistical considerations identified in the protocol and, where considerations are substantially different, they will be identified as such. Any deviations from this analysis plan will be described in the clinical study report (CSR). Any post-hoc, or unplanned analyses performed that are not specified in this SAP will be clearly identified in the CSR. This plan is developed and finalized prior to database lock of the clinical database. This SAP is written with consideration of the recommendations outlined in the International Conference on Harmonisation (ICH) E9 Guideline (Guidance for Industry: Statistical Principles for Clinical Trials) and on the ICH E3 Guideline (Guidance for Industry: Structure and Content of Clinical Study Reports).

Interim data may be analyzed and reported in an interim CSR at any timepoint (including at the primary completion date [PCD]) before the final ORR collection are complete. The following CSRs will contain any updated data collected after the interim CSR cutoff date.

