A modified toxicity probability interval (mTPI) method, targeting a DLT rate of 25% and an acceptable equivalence interval of 20% 30% will be utilized for dose escalation in Part 1. All patients will also be monitored closely for DLTs until the end of Cycle 1. All patients will be monitored for late toxicities following the initial DLT period up to Day 60 from first dose. Once a dose level has been declared safe following the 60-day evaluation, patients at lower dose levels who have completed the 60-day late toxicity observation period may escalate to the next higher dose level, if criteria outlined in Section 3.1.4.1 of the protocol have been met. Additional intra patient dose escalations will also be permitted after a minimal interval of 60 days. No crossover is allowed, however, between patients assigned to monotherapy PF-06863135 and the different combination regimens.

For safety reasons, a staggered enrollment strategy will be applied for Parts 1 and 1.1 at each dose level; the first patient will be dosed on C1D1 and observed for 48 hours. If no safety concerns arise during this 48-hr. period, subsequent patients will be enrolled into the same dose level. All patients in Part 1 and Part 1.1 will be monitored closely for dose limiting toxicities (DLTs, see Section 3.2 of the protocol) during the first 21-day period for weekly dosing and 28-day period for Q2W dosing.

[figure not shown]
Following the initial dose, treatment with investigational product will continue until disease progression, subject withdrawal of consent or unacceptable toxicity occurs. A follow up visit approximately 4 weeks after the last dose for adverse event (AE) and serious AE (SAE) collection will be conducted. If the subject completes the 1 month follow up visit prior to completion of the 60-day long term DLT observation period, a follow up phone call will be completed on Day 60, and no later than Day 65. Patients found to have anti-drug antibodies (ADA) at their final study visit and an ongoing AE possibly related to ADA will be asked to return to the clinic for ADA assessment at approximately 3 month intervals (if feasible given

the underlying disease) until the adverse event or its sequelae return to baseline or stabilize at a level acceptable to the investigator and sponsor.

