5.1. Treatment Misallocations

This is an unblinded MTD dose finding study. Subjects will be included in the cohort defined by their initial dose.

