8.2.3.7. Electrocardiograms (ECG)

Triplet 12-lead ECGs will be performed per Schedule of Activities. The Day 1 triplicate ECG prior to treatment administration will be used as baseline; if it is missing, values from the ECG taken at screening will be used for baseline.

ECG assessments reported by the site will include PR, HR, QT, QRS, and QTcF. A mean score is calculated and reported for any replicate measurements having the same nominal visit. All summary statistics, analyses and figures will be based on the triplicate averaged data. Any data obtained from ECGs repeated for safety reasons after the nominal time-points will not be averaged along with the preceding triplicates.

ECG summaries will include all ECG assessments from the on-treatment period. RR will be derived from HR. Fridericia's correction (QTcF) will be based on the values collected on the CRF. QTcF will be derived from QT and HR in case QTcF is missing using the following formula:

$$QTcF(msec) = QT(msec) / \sqrt[3]{RR(sec)}$$

All ECG assessments will be listed, and those collected outside the on-treatment period will be flagged in the listing.

QTcF will be summarized by maximum on-treatment values using the following categories:

- <450 msec;
- ≥ 450 msec but ≤ 480 msec;
- >480 msec but ≤ 500 msec;
- >500 msec.

Unscheduled assessments will be utilized in addition to planned assessments. Shift tables will be provided for baseline QTcF value versus worst on-treatment value. Results of ECGS done as additional follow-up for prolonged PK $t_{1/2}$ and unscheduled ECG results will be listed but not summarized. Additionally, maximum increases from baseline (including

scheduled and unscheduled assessments) will be summarized based on the following categories:

- Change >60 msec;
- Change >30 msec but ≤ 60 msec;
- Change ≤ 30 msec.

Data listings will contain the means from a triplicate as well as the parameters from each of the 3 ECGs. Note that using the mean value may result in a participant having a measurement that is not represented by an actual ECG.

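### SAP 8.2.3 tabulates safety by initial dose over a window that continues past intra-patient dose escalation, where Protocol 9.6 censors, and the difference is not flagged

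*SAP*

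**What the plan says.** **Protocol 9.6 (Safety Analysis).** For patients who escalate, "safety analysis of their initial assigned dose will be censored at time of intra-patient dose escalation", with maintenance dose escalation as the corresponding point in Part 1.1. The section adds that every patient still contributes at least 60 days at the initial level.

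**SAP 8.2.3 (Safety Analyses).** "Data will be summarized by cohort, defined by the initial dose". The window is then fixed: "On-treatment period is defined as the time from the first dose of study intervention through the minimum of" two dates, less one day. These are 90 days after last dose (28 days for patients who finished before Protocol Amendment 8 was approved) and the start of new anticancer therapy.

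**SAP 8.2.3.7 (Electrocardiograms).** "ECG summaries will include all ECG assessments from the on-treatment period", and "QTcF will be summarized by maximum on-treatment values using the following categories".

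**SAP 5.1 and 2.1.** The SAP keeps each patient in the starting column: "Subjects will be included in the cohort defined by their initial dose". It also knows that doses can rise: "Additional intra patient dose escalations will also be permitted after a minimal interval of 60 days".

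**SAP 2 (Introduction).** The SAP takes precedence over the protocol's statistical considerations, and "where considerations are substantially different, they will be identified as such".

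**The concern.** The two documents end the initial-dose window at different points. A programmer working from the SAP has an explicit definition of the on-treatment period, a fixed dose column for each patient, and no instruction to cut or re-attribute data at escalation. Events at the higher dose would therefore appear in the lower dose's column.

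The direction of the error is predictable. Protocol 3.1.4.1 and 5.5.4 allow escalation only if no drug-related toxicity has exceeded Grade 2. If those criteria are followed, an escalated patient's first drug-related Grade 3 or worse event falls at or after the step-up, yet it would be reported against a dose the patient had left. What is at stake is the by-dose description of toxicity in the escalation parts.

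**Working it through.** No design figure is involved, so the check is mainly a comparison of texts, followed by scope and an illustration of size.

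**1. End of the initial-dose window**

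| | Protocol 9.6 | SAP 8.2.3 |
|---|---|---|
| Grouping | initial assigned dose | initial dose |
| Ends at escalation? | yes | no |
| Otherwise ends | not specified there | last dose + 90 (or 28) days, or new therapy, less 1 day |

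The SAP contains no censoring or re-attribution rule for escalation anywhere else. Its before/after convention in 8.2.3 assigns same-day adverse events to an administration; it does not move them between dose columns.

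**2. Version.** The SAP is written for Protocol Amendment 8 and the protocol in hand is Amendment 9. The Amendment 9 change list does not name Section 9.6, and the SAP amendment notes do not mention safety windowing. A version difference does not explain the gap.

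**3. Who could be affected.** Protocol 1.2.3.1 gives enrolment at the June 2022 cutoff: 23 Part 1 IV, 30 Part 1 SC, 20 Part 1.1, 15 Part 2A, 4 Part 1C and 9 Part 1D (total 101).
- The 41 patients on the full 1000 µg/kg or 76 mg regimen match 6 (Part 1 SC at 1000 µg/kg, the response denominator in Protocol 3.4) + 20 + 15. Part 1.1 patients therefore appear to have been at the top level of Protocol Table 3 already, with no higher listed level to move to.
- That leaves at most 23 IV and 30 − 6 = 24 lower-dose SC patients, plus up to 4 + 9 = 13 combination patients. Only those still on treatment when a step-up became possible count. How many actually escalated is not stated.

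**4. Earliest step-up under sequential escalation (3-week cycles).** The next level opens on Day 22, after the 21-day DLT period. The 48-hour stagger puts its later patients at Day 24. That level then needs 60 days of observation: 24 + 60 = Day 84. Nominal weekly doses fall on Days 78 and 85, so the first escalated dose is about Day 85.

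**5. Share of the SAP window after step-up (illustration only).** Window length = last-dose day + 28 (or 90) − 1; days from step-up on = window − 84. Last-dose days are assumed, with no new therapy.

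| Assumed last dose | 28-day rule | 90-day rule |
|---|---|---|
| Day 183 (6 months) | 126/210 = 60% | 188/272 = 69% |
| Day 244 (8 months) | 187/271 = 69% | 249/333 = 75% |

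If the next level had already been cleared and step-up came on Day 61, straight after the 60-day minimum, the 6-month row becomes 150/210 = 71% and 212/272 = 78%. For a patient who stops by 12 weeks the question does not arise on this sequential timetable: the last nominal dose (Day 78) precedes any step-up.

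**6. Ceiling per patient.** One patient adds at most 1/4 = 25 percentage points in a cohort of 4, or 1/6 = 17 points in a cohort of 6. It does so only for an event or worst grade not already recorded before step-up. These sizes are response denominators in Protocol 3.4, not stated safety-set sizes.

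**The case against.** The best defence is that the two rules can coexist. The SAP defines a patient-level on-treatment period, and Protocol 9.6 places a dose-attribution cut inside such a period. Protocol 9.6.2.1 and 9.6.2.2 themselves speak of the whole study period alongside the censoring rule. Protocol 9.6.2.3 likewise uses the maximum post-baseline QT interval without repeating the cut. This is right as far as it goes: the entire-study wording in SAP 8.2.3.1 and 8.2.3.2 is not evidence of conflict, and the ECG section is a place where the window is applied rather than independent proof. From Cycle 3 ECGs are taken only on Day 1 of each cycle, so few values are involved. But in the protocol the governing rule is present, whereas the SAP declares precedence and leaves it out.

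Protocol section 9 also permits the SAP to modify the protocol; only major changes to primary endpoint definitions or their analyses need an amendment. That stands. The fault is an unexplained and unflagged change, not a forbidden one, and whether it is substantial enough to trigger the SAP's own promise is a judgement.

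A reader might infer more: that the MTD or RP2D is compromised, or that most safety data sit in the wrong column. The documents do not support either. Protocol 3.1.4.1 excludes post-escalation data from MTD/MAD evaluation, the RP2D is already selected, Part 2 does not use intra-patient escalation, and the number of escalated patients is unknown.

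**Conclusion.** The discrepancy is real and should be corrected before the by-dose safety tables are programmed. As written, the SAP attributes post-escalation adverse events, laboratory abnormalities and QTcF values to a lower dose than the patient was receiving, contrary to Protocol 9.6 and without saying so.

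Its reach is narrow. It touches non-inferential, descriptive tables by initial dose, mainly Part 1 IV and lower-dose SC, and possibly Parts 1C and 1D. The Part 1.1 limb appears to be empty on the enrolment figures. If nobody escalated, nothing changes. The share-of-window figures depend on assumed treatment durations and step-up dates and show only that, for a long-treated escalated patient, most of the window could lie after step-up. They do not estimate the actual misattribution.

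**What to change.** Add to SAP 8.2.3:

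> For safety summaries by initial dose, data are censored at the first dose above the initially assigned level (in Part 1.1, above the assigned maintenance level; the planned step from priming to maintenance is not an escalation), as in Protocol 9.6. Later data stay in the aggregate summaries and are listed separately.

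Apply it to the adverse event, laboratory and ECG tables by initial dose. If full-period attribution is what the sponsor wants, say so in 8.2.3 and identify it as a departure from Protocol 9.6. No efficacy analysis needs to change.

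The cost is one SAP addition and one derived date per patient; doses and dates for each dosing period are already in the listings of SAP 8.2.3.5. The price is shorter follow-up at the initial dose, which Protocol 9.6 accepts with its 60-day minimum, and dose columns that no longer sum to the aggregate. Censoring also brings an opposite selection effect: patients who escalate should have shown no drug-related Grade 3 or worse event before the step-up. A table footnote saying this would help readers, but it goes beyond what Protocol 9.6 requires and is optional.

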26. **Adverse Event (AE) Assessments:** AEs should be documented and recorded at each visit using the National Cancer Institute Common Terminology Criteria for Adverse Events (NCI CTCAE) version 4.03. However, the severity of cytokine release syndrome (CRS) will be assessed according to the grading described by Lee et al. (2014 and 2019^{2,3} See Appendix 5) instead of CTCAE. In addition, American Society for Transplantation and Cellular Therapy (ASTCT) consensus grading of CRS and immune effector cell-associated neurotoxicity (ICANS)³ will be captured separately from the AE assessments (See Appendix 5). The time period for actively eliciting and collecting AEs and SAEs ("active collection period") for each patient begins from the time the patient provides informed consent through and including a minimum of 90 calendar days after the last investigational product administration. If the patient begins a new anticancer therapy, the period for recording non-serious AEs on the case report form (CRF) ends at the time the new treatment is started. However, any SAEs occurring during the active collection period must still be reported to Pfizer Safety and recorded on the CRF, irrespective of any intervening treatment.

27. **Concomitant Treatments:** all concomitant medications and Nondrug Supportive Interventions should be recorded on the CRF.

28. **Genetic Analysis:** Bone marrow aspirates taken on C1D1 will be evaluated at local lab for t(4;14)(p16;q32), t(14;16)(q32;q23), 17p13 deletions, t(11;14)(q13;q32), chromosome 13 deletion, ploidy category, and chromosome 1 abnormalities. If some of these cytogenetic assessments cannot be done, site should provide patient's most recent cytogenetic testing results and enter into eCRF. Sample may be taken up to 7 days before the start of study treatment.

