32. **Gene expression ribonucleic acid (RNA) profile:** gene expression associated with activation state and anti-tumor activity will be measured by RNA sequencing in bone marrow. If sample collection day coincides with days whereby investigational product is to be administered, samples will be collected prior to investigational product administration. Bone marrow sample for Cycle 1 Day 1 (C1D1) may be taken up to 7 days before study treatment; samples at 1 month or 3 months after C1D1 will be collected ±7 days; samples at 9 months after C1D1 will be collected ±14 days. When bone marrow aspirate samples are taken for disease response evaluation, samples for gene expression analysis will also be acquired.
33. **T-cell receptor (TCR) sequencing:** clonal expansion, contraction and diversity and its association with activity and durability will be assessed by deoxyribonucleic acid (DNA) sequencing of TCR in bone marrow. If sample collection day coincides with days whereby investigational product is to be administered, samples will be collected prior to investigational product administration. Bone marrow sample for Cycle 1 Day 1 (C1D1) may be taken up to 7 days before study treatment; samples at 1 month or 3 months after C1D1 will be collected ±7 days; samples at 9 months after C1D1 will be collected ±14 days. When bone marrow aspirate samples are taken for disease response evaluation, samples for TCR sequencing will also be acquired.
34. **Genomic banked biospecimens Prep D1:** If not collected on C1D1, collect at the next available time point when biospecimens are being collected in conjunction with a patient visit.
35. **One month follow-up:** At least 28 calendar days, and no more than 35 calendar days, after discontinuation of treatment, patients will return to undergo review of concomitant treatments, vital signs, and assessment for resolution of any treatment-related toxicity. Patients continuing to experience toxicity at this point following discontinuation of treatment will continue to be followed at least every 4 weeks until resolution or determination, in the clinical judgment of the investigator, that no further improvement is expected. If the patient completes the follow-up visit prior to completion of the 60 day long term dose limiting toxicity (DLT) observation period, a follow up phone call will be completed on at least Day 60, and no more than Day 65.

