2. STUDY OBJECTIVES AND ENDPOINTS

2.1. Part 1 IV and SC monotherapy Dose Escalation, Part 1.1 Priming and Maintenance Dose Escalation and Parts 1C, 1D and 1E Dose Escalation/Finding

| Primary Objectives: | Primary Endpoints: |
|---|---|
| 
 To assess safety and tolerability at increasing dose levels of PF-06863135 as monotherapy and in combination with lenalidomide, pomalidomide, or dexamethasone in successive cohorts of patients with multiple myeloma in order to estimate the Maximum Tolerated Dose (MTD) or Maximum Administered Dose (MAD) and select the Recommended Phase 2 Dose (RP2D). | 
 Number of DLTs following treatment with escalating doses of PF-06863135 as monotherapy and in combination with lenalidomide, pomalidomide, or dexamethasone. |
| Secondary Objectives: | Secondary Endpoints: |
| 
 To evaluate the overall safety profile. | 
 Adverse Events as characterized by type, frequency, severity as graded by NCI CTCAE version 4.03, timing, seriousness, and relationship to PF-06863135 treatment as monotherapy and in combination with lenalidomide, pomalidomide, or dexamethasone. The severity of CRS will be assessed according to the grading described by Lee et al. (2014 and 2019).^{2,3} See Appendix 5; Laboratory abnormalities as characterized by type, frequency, severity (as graded by NCI CTCAE version 4.03), and timing. |
| 
 To evaluate anti-myeloma activity of PF-06863135 as monotherapy and in combination with lenalidomide, pomalidomide, or dexamethasone. | 
 Objective response rate (ORR) using the international myeloma working group (IMWG) response criteria for multiple myeloma^{4,5} (see Appendix 2); Time to event endpoints: time to response (TTR), complete response rate (CRR), duration of response (DOR), duration of complete response (DoCR), duration of stable disease (DOSD), progression-free survival (PFS), overall survival (OS), as assessed by IMWG criteria for response^{4,5} (see Appendix 2); Rate of patients with no MRD after treatment with PF-06863135 using IMWG MRD criteria⁵ (see Appendix 3). |

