8.2.3.1. Adverse Events

AEs will be graded by the investigator according to the CTCAE version 4.03 and coded using the MedDRA. The focus of AE summaries will be on Treatment Emergent Adverse Events, those with initial onset or increasing in severity after the first dose of study medication. The number and percentage of subjects who experienced any AE, serious AE (SAE), treatment related AE, and treatment related SAE will be summarized according to worst toxicity grades. The summaries will present AEs both on the entire study period. The Safety Analysis Set will be used.

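### SAP 8.2.3 counts adverse events to 28 or 90 days after last dose depending on when the patient completed the trial, so AE percentages by dose cohort lack a common window and the switch is keyed to the wrong date

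*SAP*

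**What the plan says.** SAP 8.2.3 defines the on-treatment period as running from first dose to the day before the earlier of two dates: "90 days (28 days for patients who completed the trial prior to approval of PA8 in June 2021) after last dose", and the "start day of new anticancer therapy". On grouping it says: "Data will be summarized by cohort, defined by the initial dose". SAP 8.2.3.1 reports counts and percentages of patients by worst grade, for treatment-emergent events, meaning "those with initial onset or increasing in severity after the first dose of study medication". That definition has no end date; the end comes from 8.2.3. The SAP plans no exposure-adjusted rate, common-window table or other sensitivity analysis for the change of window.

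The Part 1 primary objective (Protocol 2.1) begins "To assess safety and tolerability at increasing dose levels of PF-06863135". Dose levels opened in order: IV 0.1 to 50 µg/kg, then SC 80 to 1000 µg/kg, then the priming cohorts, then Part 2A (Protocol Summary and 3.1.1 to 3.4).

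On collection, Protocol 8.1.4 and Schedule of Activities A footnote 26 require active AE elicitation "through and including a minimum of 90 calendar days after the last investigational product administration". Footnote 35 of the same schedule supplies one routine post-treatment visit: "At least 28 calendar days, and no more than 35 calendar days, after discontinuation of treatment, patients will return". Schedules B and C have 28-, 90- and 120-day follow-up columns. The amendment history records that Amendment 8 (June 2021) extended AE assessment to 90 days. SAP 2.1 still describes an AE and SAE collection visit about 4 weeks after the last dose.

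**The concern.** A crude percentage depends on how long each patient is watched. Here the length of watching depends on the calendar, and the calendar is linked to dose because levels were opened in ascending order. Patients from early, low-dose cohorts are more likely to have finished before June 2021 and to have 28 days counted. Patients from later cohorts are more likely to have 90. Part of any rise in AE percentage across cohorts could then come from the window and not from the drug. Late-onset categories that the SAP singles out, such as infection, neuropathy and hypogammaglobulinaemia, are the most exposed.

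The trigger adds a second problem. Protocol 6.6 says that stopping treatment is not leaving the study, and survival follow-up continues until death or the study limit. A patient whose drug stopped well before PA8, but who was still being followed for survival in June 2021, has not completed the trial and is assigned 90 days. For that patient, days 29 to 90 would be analysed as observed time although AE collection was not then planned to run that far.

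**Working it through.** The plan gives no figure for this effect, so there is none to reproduce. The check asks how far the window alone could move a crude percentage when the drug effect is identical.

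**Inputs**
- Windows: 28 and 90 days (SAP 8.2.3). The one-day subtraction applies to both, so the difference is 90 − 28 = 62 days.
- Time on drug, T: 4 to 12 weeks (28 to 84 days), the SAP 2.1 estimate. A long scenario uses the median PFS at full dose, 10.4 months (Protocol 1.2.3.2), as a proxy: 10.4 × 30.4375 ≈ 317 days.
- Assumed, because the documents do not give them: incidence of 20% under the 28-day window; event hazard from day 28 to day 90 after last dose at 0 to 100% of the on-treatment hazard; share of each cohort on 90 days from 0 to 100%.

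**Formula**
With a constant first-event hazard λ up to 28 days after last dose, set λ = −ln(1 − 0.20)/(T + 28). If the later hazard is r × λ over d extra days, incidence under the long window is 1 − exp[−λ(T + 28) − rλd].

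For T = 84: λ = 0.2231/112 = 0.00199 per day. With r = 1 and d = 62, incidence is 1 − exp(−0.00199 × 174) = 29.3%, which is 9.3 points above 20%.

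**Added percentage points, d = 62**

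| Time on drug | Time-at-risk ratio | r = 1 | r = 0.5 | r = 0.25 | r = 0 |
|---|---|---|---|---|---|
| 28 days | 118/56 = 2.11 | 17.5 | 9.3 | 4.8 | 0 |
| 84 days | 174/112 = 1.55 | 9.3 | 4.8 | 2.4 | 0 |
| 317 days | 407/345 = 1.18 | 3.1 | 1.6 | 0.8 | 0 |

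If new therapy cuts the extra observation to 30 days, the 84-day row becomes 4.6, 2.4, 1.2 and 0.

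**Mixed cohorts**
At T = 84 and r = 1, if a share f of a cohort is on the 90-day window, incidence is 29.3f + 20(1 − f): 22.3% at f = 0.25, 24.6% at 0.5 and 27.0% at 0.75, up to rounding. Only the difference in f between cohorts produces a spurious trend.

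**What does not move**
The DLT period ends with Cycle 1 (Cycles 0 and 1 with priming). DLTs and other Cycle 1 events, including first-dose CRS, change by 0.

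**Schedule A**
After the day 28 to 35 visit, 90 − 35 = 55 days of the required collection period have no routine AE visit. Four-weekly follow-up applies only to patients with continuing toxicity, and the 3-monthly call is specified for survival and later therapy.

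**The case against.** A reader might infer that AE incidence is in fact inflated in the higher-dose cohorts. The documents do not show that, for four reasons.

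- The switch is on trial completion and not on dose, and enrolment was already complete at PA8. No cohort's share on each window is reported. Read literally, early low-dose patients still in survival follow-up also get 90 days, and high-dose patients who died or left before June 2021 get 28.
- The late AE hazard is not given. The window stops at new anticancer therapy, and long treatment at full dose shrinks the effect.
- Another bias may run the other way. Protocol 9.6 censors safety data at intra-patient escalation. SAP 8.2.3 groups by initial dose without repeating this, so events at an escalated dose could be counted in the lower-dose cohort.
- SAP 6.5 plans no comparison between dose groups, and 8.1 calls the summaries non-inferential.

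A reader might also infer that the RP2D choice is undermined. It is not: Protocol 3.4 records it as already selected from preliminary Part 1 data.

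All this stands against a claim of demonstrated inflation. It does not remove the unequal window. By-dose percentages are the intended safety output even without a test, and readers will compare them. The literal reading of the trigger does not restore balance either: it gives early patients 90 nominal days with AE collection planned for only about 4 weeks.

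Matching the analysis window to the collection period is defensible, so the 90-day tables should stay. The protocol's split into Cycle 1 and later cycles would give one unaffected view. SAP 6.2 keeps by-cycle summaries, but SAP 8.2.3.1 mentions only the entire study period.

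**Conclusion.** The point holds as a built-in difference in ascertainment, not as a shown bias. Taken alone, the longer window can add events but never remove them, so it can raise AE percentages in later, mostly higher-dose cohorts. At 20% incidence under the 28-day window the addition is 0 to 9.3 points at 12 weeks on drug, up to 17.5 at 4 weeks, and at most 3.1 at about 317 days. These figures rest on a constant hazard on drug, an assumed late hazard, no new therapy, and one cohort wholly on each window. Real differences would be smaller where cohorts are mixed. The net direction across all by-dose tables is not fixed. It is also an inference from 8.2.3 that the treatment-emergent AE tables are limited to the on-treatment period, because 8.2.3.1 does not say so. The mis-keyed trigger and the gap in Schedule A can be read directly from the documents and need no assumption about hazards.

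**What to change.** In SAP 8.2.3:
- Wherever dose cohorts appear side by side, add an AE table on one window for everyone: first dose to the earlier of 28 days after last dose or the day before new anticancer therapy. The window contribution is then zero by construction.
- Key the 28/90-day switch to the date of last dose relative to PA8, not to trial completion. State which PA8 date applies, since Protocol 12.1 requires ethics approval before an amendment is implemented.
- Report the number of patients per cohort under each window.
- Keep the 90-day tables, so that no collected event leaves the main output.

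In the protocol, reconcile Schedule A footnote 26 with its visit table, for example by eliciting AEs at the existing 3-monthly survival call.

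The cost is SAP wording and one extra run of the AE tables. The call already exists.
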